6.1.3 Laboratory Procedures/Assessments

Details regarding specific laboratory procedures/assessments to be performed in this trial are provided below Laboratory Safety Evaluations (Hematology, Chemistry and Urinalysis).

Laboratory tests for hematology, chemistry, urinalysis, and others are specified in Table 5.

Table 5 Laboratory Tests

Hematology	Chemistry	Urinalysis	Other
Hematocrit	Albumin	Blood	Serum β -human chorionic gonadotropin†
Hemoglobin	Alkaline phosphatase	Glucose	(β-hCG)†
Platelet count	Alanine aminotransferase (ALT)	Protein	PT (INR)
WBC (total and differential)	Aspartate aminotransferase (AST)	Specific gravity	aPTT
Red Blood Cell Count	Lactate dehydrogenase (LDH)	Microscopic exam (If abnormal)	Total thriiodothyronine (T3)
Absolute Neutrophil Count	Carbon Dioxide ‡	results are noted	Free tyroxine (T4)
Absolute Lymphocyte Count	$(CO_2 \text{ or biocarbonate})$	Urine pregnancy test †	Thyroid stimulating hormone (TSH)
	Uric Acid		РК
	Calcium		
	Chloride		Blood for correlative studies
	Glucose		
	Potassium		
	Sodium		
	Magnesium		
	Total Bilirubin		
	Direct Bilirubin (If total bilirubin is elevated above the upper limit of normal)		
	Total protein		
	Blood Urea Nitrogen		

‡ If considered standard of care in your region.

6.1.3.1 Withdrawal/Discontinuation

When a subject discontinues/withdraws prior to trial completion, all applicable activities scheduled for the final trial visit should be performed at the time of discontinuation. Any adverse events which are present at the time of discontinuation/withdrawal should be followed in accordance with the safety requirements outlined in Section 6.2 - Assessing and Recording Adverse Events.

6.1.4 Visit Requirements

Visit requirements are outlined in Section 5.0 - Trial Flow Chart. Specific procedure-related details are provided above in Section 6.1 - Trial Procedures.

6.1.4.1 Screening

6.1.4.1.1 Screening Period

The screening period begins upon signing consent and includes evaluation of available tissue specimen for study-related, central review, any ancillary/staging/laboratory testing or other evaluations prior to Cycle 1 Day 1 of study therapy. The screening period may last up to 42 days (6 weeks).

Laboratory studies collected within the 42 days prior to study drug start, for standard of care purposes, may be used to satisfy screening requirements and do not need to be repeated at screening. In addition, if lab studies are done within 7 days of cycle 1 day 1, they do not need to be repeated for study purposes. Archival bone marrow aspirate /biopsy data is acceptable if performed within the 6 months prior to signing consent.

6.1.4.2 Treatment Period

The treatment period begins with the first administration of study treatment, and is designated as Cycle 1 Day 1.

- **6.1.5 Induction phase:** The induction phase will consist of four cycles lasting 3 weeks: pembrolizumab 200 mg on day 1 every 3 weeks, and rituximab (Arms A and B) or obinutuzumab (Arm C) on day 1 (after pembrolizumab) x 4 doses (Cycle 1 day 1, 8, 15, and cycle 2 day 1).
- **6.1.6 Extended Therapy Phase:** Patients with at least a partial response may continue on extended therapy: pembrolizumab 200 mg day 1 every 3 weeks for up to 2 years maximum of 35 infusions.) In addition, for arm C, patients with stable disease or better, who are experiencing clinical benefit in the judgment of the investigator, may receive up to 6 more doses of obinutuzumab every 3 months (cycles

5,9,13,17,21,and 25) in combination with pembrolizumab every 21 days, up to 35 cycles.

6.1.6.1 Discontinuation of Study Therapy after CR: Patients may elect to stop therapy during the extended therapy phase, if in CR after at least 8 cycles (24 weeks) of pembrolizumab therapy. CR may be defined by CT, PET-CT, either in conjunction with biopsy when applicable (including marrow assessment). These patients are eligible for the Second Course period as in section 6.1.6.2 if no cancer treatment was administered since the last dose of pembrolizumab, the subject meets the safety parameters listed in the Inclusion/Exclusion criteria, and the trial is open. Ninety days after receiving the last dose of pembrolizumab, subjects in CR who are potential retreatment candidates may convert to standard of care surveillance visits, while remainingeligible for the Second Course period as in 6.1.6.2.

6.1.6.2 Second Course (retreatment) Period:

Subjects who elect to stop study therapy for proven CR are eligible for up to one year of additional pembrolizumab therapy, and for Arm C patients q12 week obinutuzumab (maximum of 6 courses q 3 months, and 10 total doses, including all prior doses) if they progress after stopping study treatment.

This retreatment is termed the Second Course Phase of this study and is only available if the study remains open and the subject meets the following conditions:

• Stopped therapy after receiving at least 8 cycles (24 weeks), and attaining an investigator-determined CR (CT, PET-CT, and/or biopsy-proven CR).

AND

• Experienced an investigator-determined confirmed radiographic disease progression after stopping their initial treatment with pembrolizumab

• Did not receive any anti-cancer treatment since the last dose of pembrolizumab

- Has a performance status of 0 or 1 on the ECOG Performance Scale
- Demonstrates adequate organ function as per Inclusion Criteria

• Female subject of childbearing potential should have a negative serum or urine pregnancy test within 72 hours prior to receiving retreatment with study medication.

• Female subject of childbearing potential should be willing to use 2 methods of birth control or be surgically sterile or abstain from heterosexual activity for the course of the study until at least 12 months after the last dose of study therapy (Reference Section 4.4.2). Subjects

of child bearing potential are those who have not been surgically sterilized or have been free from menses for > 1 year.

• Male subject should agree to use an adequate method of contraception starting with the first dose of study therapy until at least 12 months after the last dose of study therapy.

• Does not have a history or current evidence of any condition, therapy, or laboratory abnormality that might interfere with the subject's participation for the full duration of the trial or is not in the best interest of the subject to participate, in the opinion of the treating investigator.

Subjects who restart treatment will be retreated at the same dose and dose interval as when they last received study therapy with pembrolizumab and obinutuzumab. Treatment will be administered for up to one additional year, with CT restaging performed every 3 months.

6.1.6.3 Off-Study Visit

The mandatory Off-Study Visit should be conducted approximately 90 days (+/- 7days) after the last dose of pembrolizumab irrespective of reason it was stopped, but may be done earlier for patients embarking on additional anti-lymphoma therapy. All AEs that occur prior to the Off-Study Visit should be recorded. Subjects with an AE of Grade > 1 will be followed until stabilization or resolution of the AE to Grade 0-1 or until the beginning of a new anti-neoplastic therapy, whichever occurs first. SAEs that occur within 90 days of the end of treatment or before initiation of a new anti-cancer treatment should also be followed and recorded.

The off-study visit will include laboratory studies (CBC diff, CMP, LDH), medical history, physical exam, remission status, concomitant medications, adverse events, and documentation of any ECI and subsequent management.

After the off-study visit, additional surveillance will be conducted as per routine standard of care. Every effort should be made to collect information regarding disease status until the start of new anti-neoplastic therapy, disease progression, death, or end of study. Information regarding post-study anti-neoplastic treatment will be collected if new treatment is initiated.

Patients who initiated retreatment require a second off-study visit, to be performed as above 90 days after their last dose of pembrolizumab (+/-7 days).

6.2 Assessing and Recording Adverse Events

Adverse events will be recorded, and ECI and SAE's reported, from the time of signed consent and for up to 90 days after the last dose of pembrolizumab is administered.

An adverse event is defined as any untoward medical occurrence in a patient or clinical investigation subject administered a pharmaceutical product and which does not necessarily have to have a causal relationship with this treatment. An adverse event can therefore be any

unfavorable and unintended sign (including an abnormal laboratory finding, for example), symptom, or disease temporally associated with the use of a medicinal product or protocol-specified procedure, whether or not considered related to the medicinal product or protocol-specified procedure. Any worsening (i.e., any clinically significant adverse change in frequency and/or intensity) of a preexisting condition that is temporally associated with the use of the Merck product, is also an adverse event. Progression of the cancer under study is not considered an adverse event.

Laboratory abnormalities will only be recorded if grade 3 or higher, possibly related to study therapy, and clinically significant in the judgment of the investigator. Merck product includes any pharmaceutical product, biological product, device, diagnostic agent or protocol-specified procedure, whether investigational (including placebo or active comparator medication) or marketed, manufactured by, licensed by, provided by or distributed by Merck for human use.

Adverse events may occur during the course of the use of Merck product in clinical trials or within the follow-up period specified by the protocol, or prescribed in clinical practice, from overdose (whether accidental or intentional), from abuse and from withdrawal.

Adverse events may also occur in screened subjects during any pre-allocation baseline period as a result of a protocol-specified intervention, including washout or discontinuation of usual therapy, diet, placebo treatment or a procedure.

All adverse events will be recorded from the time the consent form is signed through 90 days following cessation of MK-3475 treatment and at each examination on the Adverse Event worksheets.

6.3 Definition of an Overdose for This Protocol and Reporting of Overdose to Merck

For purposes of this trial, an overdose will be defined as any dose exceeding the prescribed dose for MK-3475 by 20% over the prescribed dose. No specific information is available on the treatment of overdose of MK-3475. In the event of overdose, MK-3475 should be discontinued and the subject should be observed closely for signs of toxicity. Appropriate supportive treatment should be provided if clinically indicated.

If an adverse event(s) is associated with ("results from") the overdose of a Merck product, the adverse event(s) is reported as a serious adverse event, even if no other seriousness criteria are met.

If a dose of Merck's product meeting the protocol definition of overdose is taken without any associated clinical symptoms or abnormal laboratory results, the overdose is reported as a nonserious Event of Clinical Interest (ECI), using the terminology "accidental or intentional overdose without adverse effect." All reports of overdose with and without an adverse event must be reported within 2 business days of investigator knowledge Merck Global Safety. (Attn: Worldwide Product Safety; [contact])

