2.2 Secondary Objectives

(1) To evaluate the safety and tolerability of the combination of CD20-directed therapy and pembrolizumab

(2) To evaluate 2-year progression-free survival (PFS) and overall survival (OS) in each treatment group

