4.2.1.2 Dose Modification (Escalation/Titration/Other)

Adverse events (both non-serious and serious) associated with pembrolizumab exposure may represent an immunologic etiology. These adverse events may occur shortly after the first dose or several months after the last dose of treatment. Pembrolizumab must be withheld for drug-related toxicities and severe or life-threatening AEs as per Table 3 below. See Section 5.6 for supportive care guidelines, including use of corticosteroids. Table 3 lists dose modifications for pembrolizumab. Note that dose modification of rituximab, and management of rituximab-related infusion reactions, will follow institutional standard of care and investigator/sub-investigator discretion and is not specified in this protocol.

Table 3 Dose modification and toxicity management guidelines for immune-related AEs associated with pembrolizumab

Toxicity	Hold Treatment For Grade	Timing for Restarting Treatment	Treatment Discontinuation	
Diarrhea/Colitis	Z-3 Toxicity resolves to Grade 0-1 to reduce corticosteroid t		Toxicity does not resolve within 12 weeks of last dose or inability to reduce corticosteroid to 10 mg or less of prednisone or equivalent per day within 12 weeks	
	4	Permanently discontinue	Permanently discontinue	
AST, ALT, or	2	Toxicity resolves to Grade 0-1	Toxicity does not resolve within 12 weeks of last dose	
Increased Bilirubin 3-4		Permanently discontinue (see exception below) ^a	Permanently discontinue	
Type 1 diabetes mellitus (if new onset) or Hyperglycemia	T1DM or 3-4	Hold pembrolizumab for new onset Type 1 diabetes mellitus or Grade 3-4 hyperglycemia associated with evidence of beta cell failure	Resume pembrolizumab when patients are clinically and metabolically stable	
Hypophysitis	2-4	Toxicity resolves to Grade 0-1. Therapy with pembrolizumab can be continued while endocrine replacement therapy is instituted	Toxicity does not resolve within 12 weeks of last dose or inability to reduce corticosteroid to 10 mg or less of prednisone or equivalent per day within 12 weeks	
Hyperthyroidism	3	Toxicity resolves to Grade 0-1	Toxicity does not resolve within 12 weeks of last dose or inability to reduce corticosteroid to 10 mg or less of prednisone or equivalent per day within 12 weeks	
	4	Permanently discontinue	Permanently discontinue	

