6.8.1 Sponsor-Investigator Responsibility for Reporting Adverse Events

The sponsor-investigator is required to report all problems, events and information that require prompt reporting to the IRB within ten (10) calendar days of learning of the problem.

Adverse events will be reported from the time of signing of consent up until 90 days following the last dose of MK-3475.

Laboratory abnormalities will be recorded as adverse events only if they meet the following criteria: the abnormality is symptomatic, warrants a change to study drug dosing, is designated clinically significant by the investigator, or reaches severity of grade 3 or higher (asymptomatic lab values < grade 3 will not be recorded as AEs).

If a problem, event or information is determined to be an unanticipated problem involving risks to participants or others, it will be reviewed by the convened IRB, appropriate steps will be taken and it will be reported to appropriate institutional and governmental officials as provided under applicable law.

For the purposes of this protocol, the terms Adverse Event, Serious Adverse Event (Related, Possibly Related or Unexpected) and Unanticipated Problem are defined in accordance with Fred Hutchinson Cancer Research Center Institutional Review Board Policy 2.6, version 6.03.

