7.0 STATISTICAL ANALYSIS PLAN

This study administers therapy to two groups of patients, relapsed/refractory FL and relapsed/refractory DLBCL.

Subjects who fail to complete study therapy or withdraw consent before the first response assessment for reasons other than disease progression, death, SAE, or drug-related adverse events will be replaced, to allow response assessment in accordance with study stopping rules. The first group (Arm A) includes patients with relapsed or refractory follicular lymphoma, and will include at least 9 patients with rituximab-refractory disease.

The second group (Arm B) consists of patients with relapsed/refractory diffuse large B-cell lymphoma ineligible for, or failing to respond to or progressing, after autologous stem cell transplantation.

These groups will employ independent rules, using Simon's two-stage design, and accrual will be suspended for review if futility thresholds are met. Two-stage designs which limit the maximum sample size will be considered. Once enrollment is suspended, the nature of events to leading to stopping will be assessed by the Principal Investigator and reported to institutional regulatory authorities, in accordance with the institutional Data Safety Monitoring Plan. The institutional Data Safety Monitoring Committee will determine whether any further accrual may proceed. Statistical analysis will entail descriptive statistics. Categorical variables will be summarized by number and percentage, and continuous variables will be summarized by min/median/max/mean/sd, respectively. Overall response rate, and response quality, will be evaluated according to CT criteria and PET/CT in relevant patients, as per the 2014 Lugano criteria.²⁸ PFS/OS distribution will be estimated and Kaplan-Meier curves will be presented. Log-rank testing and Cox proportional hazard regression models might be applied to evaluate the association between survival endpoints and prognostic factors. To compare continuous variable in the correlative studies, student's t-test and regression analysis might be applied if deemed appropriate.

Subjects who fail to complete study therapy before the first response assessment for reasons other than disease progression, death, SAE, or drug-related adverse events will be replaced, to allow response assessment in accordance with study stopping rules.

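### Sections 6.2 and 6.8.1 set incompatible rules for recording laboratory abnormalities as adverse events, so the descriptive safety counts depend on which section is followed

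*Combined protocol and SAP*

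**What the plan says.** Section 6.2 sets a rule in which every condition must be met: "Laboratory abnormalities will only be recorded if grade 3 or higher, possibly related to study therapy, and clinically significant", with significance left to the investigator. The same section defines an adverse event to include an abnormal laboratory finding, "whether or not considered related to the medicinal product or protocol-specified procedure".

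Section 6.8.1 sets a rule in which one condition is enough: "the abnormality is symptomatic, warrants a change to study drug dosing, is designated clinically significant by the investigator, or reaches severity of grade 3"; grades above 3 also qualify. It closes with a parenthesis: "asymptomatic lab values < grade 3 will not be recorded as AEs".

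Each rule is worded as exclusive, and no text ranks one above the other.

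Three other places bear on the point:
- Section 4.2.1.2: "Pembrolizumab must be withheld for drug-related toxicities and severe or life-threatening AEs as per Table 3 below". Table 3 lists grade 2 AST, ALT or bilirubin elevation among the grades for which treatment is held.
- Section 2.2, first secondary objective: "To evaluate the safety and tolerability of the combination of CD20-directed therapy and pembrolizumab".
- Section 7.0: the analysis is descriptive. "Categorical variables will be summarized by number and percentage".

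**The concern.** A count of laboratory AEs needs one definition of what is counted. With two, the number and percentage reported for the safety objective depend on the section the study team followed, and a reader of the results could not tell which.

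Section 6.2 raises two further problems. It makes the investigator's view on causality a condition for entry into the data. In an open-label trial with no control group, nothing else in the data offsets that judgement. It also sets a grade 3 floor, although Table 3 acts on some laboratory findings at grade 2. A patient could have pembrolizumab held for a liver value with no laboratory AE to explain the hold.

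**Working it through.** The plan gives no figure on this point and no sample-size formula applies. The check compares the rules as logical statements.

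**Attributes (each yes or no), from 6.2 and 6.8.1:** G = grade 3 or higher; R = possibly related; C = clinically significant; S = symptomatic; D = warrants a dosing change. Five attributes give 2^5 = 32 combinations.

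**Rules:**
- 6.2: G and R and C.
- 6.8.1, list alone: S or D or C or G.
- 6.8.1, parenthesis read as an exclusion: the list, but not when both S and G are absent. This reduces to G or S.

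**Counts:**
- 6.2 fixes three attributes and leaves two free: 2^2 = 4.
- The 6.8.1 list fails only when S, D, C and G are all absent, with R free: 32 - 2 = 30.
- 6.8.1 with the exclusion fails when S and G are both absent, with three attributes free: 32 - 2^3 = 24.
- All 4 combinations recorded by 6.2 contain G, so both readings of 6.8.1 record them. The rules are therefore nested, and they disagree on 30 - 4 = 26 or 24 - 4 = 20 combinations.
- Of the 16 combinations with D present, 6.2 records 2 (G, R and C fixed, S free), the 6.8.1 list records 16, and the exclusion reading records 16 - 4 = 12.

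These are counts of logical cases. They say nothing about how often each case occurs.

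**Cases side by side:**

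| Laboratory abnormality | 6.2 | 6.8.1, list | 6.8.1, exclusion reading |
|---|---|---|---|
| Grade 3, related, significant | recorded | recorded | recorded |
| Grade 3, significant, judged unrelated | not | recorded | recorded |
| Grade 3, related, judged not significant | not | recorded | recorded |
| Grade 2 AST rise, symptomatic, leads to a hold | not | recorded | recorded |
| Grade 2 AST rise, asymptomatic, leads to a hold | not | recorded | not |

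Two results follow. First, the relatedness condition in 6.2 contradicts that section's own AE definition, and it sits badly with Table 6, where relatedness is scored for each event and one of the answers is no. Second, if the 6.8.1 parenthesis is an exclusion, the dosing-change and clinical-significance criteria have no effect, because the rule reduces to grade 3 or higher, or symptomatic. Adopting 6.8.1 unchanged would therefore leave the last row of the table unsettled.

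**The case against.** The strongest reply is that little is truly lost, because other routes exist:
- Table 3 concerns immune-related AEs, and the guidance in 4.3.3 applies once the investigator attributes the event to pembrolizumab. A grade 2 liver event that leads to a hold may thus be entered as a clinical immune-related event.
- Section 6.6 reports serious events whether or not related.
- Section 6.7 reports combined transaminase and bilirubin elevations on the same basis.
- The flow chart has CBC and chemistry drawn on day 1 of each cycle, so the values still exist.

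This stands in part. A reader might infer that no grade 2 hold is ever recorded under 6.2, or that unrelated grade 3-4 values vanish; the routes above rule out both. The gap is narrower: non-serious abnormalities handled purely as laboratory findings. The other routes do not close it. The liver event of clinical interest needs both elevations together (with alkaline phosphatase below twice the upper limit of normal), SAE reporting covers serious events only, and entry as a clinical event is possible but nowhere required for a hold.

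The parenthesis in 6.8.1 can also be read as a gloss on the grade criterion just before it, meaning that values below grade 3 do not qualify on grade alone. That reading is fair, so the parenthesis is ambiguous and not a plain self-contradiction.

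A further objection is that 6.8.1 as the sole rule could overcount. Table 1 sets no lower limit at entry for cytopenia from marrow involvement, and 6.8.1 carries no baseline condition, so stable disease-related cytopenias of grade 3 or higher could be logged as AEs. This stands, and the fix has to deal with it.

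**Conclusion.** The two rules are incompatible and should be reconciled. A reader might call them opposite; they are not, since 6.2 is a strict subset of 6.8.1. The direction is therefore certain: following 6.2 can only lower the laboratory AE count. That is a downward bias in the reported rates only if 6.2 is the section in use, which the documents do not say.

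The size in patients cannot be stated. The documents give no rate of laboratory abnormalities and no share judged unrelated or not significant, so any patient count would only restate its own assumptions. Nor do the documents show that staff at this single center apply different sections.

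The effect is confined to the descriptive safety summaries for the first secondary objective. The response-rate analysis and the two-stage designs are untouched. The suspension boundaries in 7.2 count non-progression deaths and SAEs, so non-serious laboratory AEs do not drive them directly.

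**What to change.** 1. Delete the laboratory sentence in 6.2 and refer to 6.8.1 as the single recording rule.
2. Limit the 6.8.1 parenthesis to asymptomatic values below grade 3 that neither change study drug dosing nor are clinically significant.
3. State that an abnormality present at baseline counts only if it worsens, in line with how the AE definition in 6.2 treats preexisting conditions.
4. Record relatedness as an attribute of each event, not as a condition for recording it.
5. Apply the single rule to the laboratory values already collected before safety is summarised.

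This concerns recording only and changes no dose, hold or clinical rule.

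The cost is a wording amendment and some retrospective review of laboratory data. Grade and dosing changes can largely be read from existing records; symptoms and clinical significance need investigator judgement after the fact, over up to 35 cycles per patient and up to 62 patients. Reported AE rates may rise slightly.
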